- The extent to which the Healthdot monitoring method can be successfully carried out by the healthcare employees
- Amount of manual spot checks per hospital admission day per patient
- The perception among nursing staff given the satisfactory and agreeableness regarding workload.
- Relation between device false alarms (noise) and correct alarms based on the alarming protocol.
- Number of unexpected events that occur during or result from the use of the Healthdot medical device.
- The amount of time needed to perform and process a complete manual spot check or digital monitoring check.
- Cost-effectiveness analysis based on the duration of admission, the associated admission costs and the monitoring method
- Advanced algorithm analyses for improved monitoring protocols

Project design:

This project is a 6 months monocenter prospective cohort at the Catharina hospital in the Netherlands. Every patient admitted to the one surgery department will receive a Healthdot. Implementation of the Healthdot will be performed stepwise. During phase 1 (month 1-3, the pre-implementation phase), the current standard method of care with manual spot checks and EWS will be continued. During this phase Healthdots will be applied only for training purposes in preparation to the implementation phase, phase 2 (month 3-6). This phase consists of primarily Healthdot monitoring and manual spot checks only if indicated. After these 6 months, the implementation will be evaluated and optimized and potentially extended.

Participants:

The main research population for answering the research objectives are the nurses and physicians working at the specific surgical ward at the Catharina hospital. In total around 500 patients, 250 during each phase, admitted to one surgical ward at the Catharina hospital will participate and receive a Healthdot as the new standard of care. These patients will sign informed consent for use of anonymized data. This population differs in age, gender, admission cause, admission duration and comorbidities but reflects the demographics of the general population on this ward which is essential to investigate implementation and prevent selection bias.

Main implementation study parameters/endpoints:

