7. METHODS

a. Study parameters/endpoints

i. Main study parameter/endpoint

Primary parameters and endpoints

Evaluation of the implementation of a continuous monitoring method on the surgical ward

- Fidelity: The usability and degree of implementation of the Healthdot at the surgical ward
 - Measured with the System usability scale (SUS), Score > 68 at M6 (8, 26)

- Acceptability: The workload regarding the amount of spot checks in addition to the standard monitoring.
 - Calculated with data from the electronic patient file records. Success in case of average reduction of 20% at M6 compared to M3

ii. Secondary study parameters/endpoints (if applicable)

Secondary parameter and endpoints

- Adoption: The intention and attitude towards the use of the Healthdot monitoring method.
 - Measured with evidence-based practise attitude scale (EBPAS) (9, 10).
- Feasibility: The extent to which the Healthdot monitoring method can be successfully carried out by the healthcare employees.
 - Measured with a thematic analysis (Braun and Clark) with core group (11).
- Acceptability: Amount of manual spot checks per hospital admission day per patient
 - \circ Calculated with data from the electronic patient file records.
- Acceptability: The perception among nursing staff given the satisfactory and agreeableness regarding workload.
 - Measured with the integrated workload scale (IWS) (12, 13).
- Appropriateness: Relation between device false alarms (noise) and correct alarms based on the alarming protocol.
 - Measured as signal to noise ratio (SNR)
- Appropriateness: Number of unexpected events that occur during or result from the use of the Healthdot medical device. Measured as adverse device events (ADE)
- Feasibility: The amount of time needed to perform and process a complete manual spot check or digital monitoring check. Measured manually.
- Costs: Cost-effectiveness analysis based on the duration of admission, the associated admission costs and the monitoring method
- Advanced algorithm analyses for improved monitoring protocols with advanced AI software

iii. Other study parameters (if applicable)

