Additional anonymized data will, in case of informed consent, be collected from the electronic patient file such age, gender, reason for admission, medical history, duration of admission, complications and laboratory results. This additional data will be used to relate the primary and secondary results to any influencing factors/ baseline characteristics and potentially correct for these factors.

Variables eCRF

Characteristic	Input
Indication	Open
Type of invasive interventions/surgery	Open
Gender	M/F
Age	Open
BMI	Kg/m2
Comorbidities	
Charlson comorbidity index	Charlson Comorbidity Index (CCI) - MDCalc
Hospital stay	
Admission date	D/M/Y
Discharge date	D/M/Y
Elective or emergency	Open
Complications	
Clavien-Dindo classification	Grade I-V
Complications type	Cardiac, Pulmonary, Kidney failure,
	infectious, traumatic, surgical related
	(perforation, leakage, bleeding)
Urgent consultations (SIT) during	0-99
hospitalization	
ICU admission	Yes/no
Mortality <30 days	Yes/no
Re-admission < 30 days	Yes/no
Fidelity	
Total minutes monitored	Min
Amount of heart rate measurements	Total number per admission
Amount of respiratory rate measurements	Total number per admission
Artefact heart rate measurements	Total number per admission
Artefact respiratory rate measurements	Total number per admission
Total amount of spot checks	Total number per admission
Device	
Premature removal of device	Yes/no
Replacement of device	Yes/no
Bijzonderheden device	Yes/no

b. Randomisation, blinding and treatment allocation

N/A

c. Project procedures

Prior to the start of the pre-implementation phase there will be a pre-implementation phase during months 1-2. This phase will consist of training the medical staff through e-learning and physical meetings. During this phase, medical staff will have the opportunity to apply the Healthdot, learn to activate it and practise with the Guardian dashboard. This phase serves as preparation for the implementation and aims to optimize the intra-structure in advance. In addition, during this phase, baseline data will be collected about the standard spot check measurements, feeling of confidence and attitude towards a change in the monitoring method. This study is a quality project and a change in standard of care. Nurses and physicians voluntarily participating in the focus group will sign informed consent for participation. Nurses not participating in the focus group but working at the surgical ward during this project will

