8. STATISTICAL ANALYSIS

The statistical analysis at professional (nurses/ physicians) level will be performed by means of descriptive statistics. Each continuous parameter is analyzed for normality by the Shapiro-Wilk test and visually by a figure. Normality-based reporting will be done using medians and interquartile ranges (IQR) or means and standard deviations (SD). Frequencies and percentages are reported for categorical data. Each continuous parameter is checked for normality by the Shapiro-Wilk test and visually by a figure. Normality-based reporting will be a figure. Normality-based reporting is performed using medians and interquartile ranges (IQR) or means and standard deviations (SD).

All analysis are performed using IBM SPSS Statistics 26.0 for Windows (IBM Armork, New York, USA) with 95% confidence interval and p < .05 as statistically significant.

The core group consisting of nurses, physicians and investigators will conduct a structured analysis into the fidelity, feasibility and acceptance of the implementation and this information is processed and objectified by means of a Braun and Clarke thematic analysis.

Objective	Instrument	Variable	Statistical test
Fidelity	SUS ^p	Continuous	Unpaired T-test/ Mann- Whitney U test
Acceptance	SC/day ^p SC/patient ^s IWS ^s	Continuous Continuous Ordinal	Descriptive statistics Descriptive statistics One-way ANOVA test
Adoption	EBPAS ^s	Continuous	Repeated measures ANOVA
Appropriateness	SNR ^s ADE ^s	Continuous Continuous	Descriptive statistics Descriptive statistics
Feasibility	Thematic analysis ^s	Nominal	Braun & Clarke thematic analysis
Time efficiency	Time measurement	Continuous	Descriptive statistics
Costs	Evaluation	Continuous	Descriptive statistics

Table 4: psychometric properties and statistical analysis

a. Other study parameters

N/A

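### The primary spot-check comparison of month 6 with month 3 has no pre-specified case-mix adjustment, so a shift in who is admitted can tip a near-threshold result either way

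*Combined protocol and SAP*

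**What the plan says.** Section 7.a.i gives the rule for the primary acceptability endpoint: "Success in case of average reduction of 20% at M6 compared to M3". The Summary repeats it, and Table 2 of Section 3 places the spot-check data at months 3 and 6. The project is a single-ward cohort, and Section 7.b marks randomisation as not applicable. About 250 patients are expected in each phase (Section 4.d), so the two periods hold different admissions.

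Section 4.a describes a mixed ward: mostly oncological surgery, with general surgical, urological and gynaecological patients, readmissions, treatment of complications and intensive care transfers. The Summary acknowledges this: "This population differs in age, gender, admission cause, admission duration and comorbidities". It presents the variety as an aid to representativeness and does not discuss it as a source of difference between periods.

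In Table 4 of Section 8, the cell for spot checks per day, spot checks per patient and the workload scale reads, in that order, "Descriptive statistics Descriptive statistics One-way ANOVA test". Both spot-check endpoints are therefore descriptive. Section 8.a, "Other study parameters", is marked N/A.

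Section 7.a.iii lists the additional variables, among them age, gender, BMI, type of surgery, elective or emergency admission and the "Charlson comorbidity index". On their use it says: "This additional data will be used to relate the primary and secondary results to any influencing factors/ baseline characteristics", and then that the analysis may "potentially correct for these factors".

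**The concern.** In phase 1 the protocol schedules three spot checks a day for every patient (Section 7.c). In phase 2 the Healthdot is the primary method and manual checks are done when indicated, for clinical doubt or at the treatment team's request. The phase 2 rate therefore depends on how ill the admitted patients are, much more directly than the scheduled phase 1 rate does.

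A pass/fail line at 20% applied to two unadjusted monthly averages cannot separate a change in monitoring practice from a change in admissions. Section 7.a.iii shows that the sponsor foresaw a possible need for correction, but Section 8 contains no analysis that would carry it out. Leaving the correction optional also means that the choice could be made after the crude result is known, on an endpoint with a sharp threshold.

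**Working it through.** **The plan's own figure.** Section 4.d expects at least 500 patients in six months from a turnover of 900 to 1000 a year. 1000 × 6/12 = 500, or 250 per phase; 900 × 6/12 = 450, or 225 per phase. The stated 500 is the upper end of that range. Monthly admissions are 900/12 = 75 to 1000/12 = 83; 80 is used below.

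**Inputs that must be assumed.** The documents give no spot-check rates by acuity, no acuity shares and no expected effect. Assumed: 3.0 checks a day for everyone in month 3 (the scheduled number); in month 6, 2.0 a day for low-acuity and 3.4 for high-acuity patients. The share of patients is treated as the share of patient-days.

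**Where the verdict flips.** With high-acuity share p, the month 6 rate is 2.0 + 1.4p, and the success threshold is 0.8 × 3.0 = 2.4.
- Flip point: p = (2.4 − 2.0)/1.4 = 28.6%.
- p = 40%: 2.56 a day, a 14.7% reduction, fail.
- p = 25%: 2.35 a day, a 21.7% reduction, success.

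**Chance variation.** Month 3 is held at 3.0 for everyone, so only the month 6 share matters. At p = 33% and n = 80, SE = √(0.33 × 0.67/80) = 5.3 points. In units of reduction this is 1.4 × 0.053/3.0 = 2.5 percentage points. At p = 33% the rate is 2.462, a 17.9% reduction (fail). One SE lower, at 27.7%, the rate is 2.388, a 20.4% reduction (success). If whole phases of 250 patients were compared, the SE would be √(0.33 × 0.67/250) = 3.0 points, or 1.4 points of reduction.

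**Other assumed rates.** With 2 and 4 checks a day in month 6, a 20% share gives a 20.0% reduction and a 30% share gives 13.3%. With 1.5 and 4, a 30% share gives 25.0% and a 40% share gives 16.7%. In both sets a 10-point shift changes the verdict.

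**Limits in each direction.**
- *No device effect, all checks counted.* If three a day is the minimum, a 20% fall needs a month 3 mean of at least 3/0.8 = 3.75 a day. With 3 and 6 checks a day by acuity, the high-acuity share must fall from 50% (mean 4.5) to 20% (mean 3.6). With 3 and 5, it must fall from 50% (mean 4.0) to 10% (mean 3.2).
- *Large true effect.* With month 3 rates of 3 versus 4, 5 or 6 a day and a 30% high-acuity share, no shift brings a true 50% reduction back to 20%. A true 25% reduction is brought back to 20% once the month 6 share reaches 39% to 52%.

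**Which adjustment works.** A Poisson model with period and acuity as main effects only was fitted to the assumed rates, with a 33% month 3 share. The standardised ratio is (0.67 × 2.0 + 0.33 × 3.4)/3.0 = 0.821.

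| Month 6 high-acuity share | Crude ratio | Main-effects ratio | Ratio standardised to the month 3 mix |
|---|---|---|---|
| 25% | 0.783 | 0.798 (success) | 0.821 |
| 40% | 0.853 | 0.838 (fail) | 0.821 |

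Main effects alone still flip the verdict, because acuity changes the rate only in month 6. Period-by-acuity terms with standardisation give the same answer both times.

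**The case against.** The strongest reply is that the plan does not ignore case mix. Section 7.a.iii commits to relating the primary and secondary results to baseline characteristics; only the correction itself is optional. That stands: adjustment is unspecified, not excluded. A reader might infer that the plan rules adjustment out, and the text does not support that.

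A reader might also infer that case mix alone could manufacture the 20% reduction. If all checks are counted, this needs a month 3 mean of at least 3.75 a day and a very large shift in admissions, and nothing in the documents points to either. It would be easier if only extra checks counted, as one wording of the endpoint suggests ("The workload regarding the amount of spot checks in addition to the standard monitoring"). With assumed rates of 0.2 versus 1, 0.2 versus 2, or 0.5 versus 2 extra checks a day, a fall in the high-acuity share from 30% to between 17% and 22% would be enough. The Summary, however, lists the primary objective as manual spot checks per admission day.

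Further points stand in part. The assumed rates were set near the threshold. Three a day is the phase 1 schedule, and extra checks are not excluded. For a ward-workload endpoint in a quality project the observed count is a legitimate target, so an adjusted ratio need not replace it. Nor is adjustment free: case-mix data exist only for consenting patients, and several variables are free text.

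None of this supplies the missing analysis.

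**Conclusion.** The concern holds as a gap in the analysis plan that should be closed. Different admissions are compared against a sharp 20% line, the only analysis named is descriptive, and correction for case mix is left open.

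The consequence is limited to results near the threshold, where a shift in admissions can tip the verdict in either direction. Under the assumed rates, chance alone moves the reduction by about 2.5 percentage points per standard error in a single month, before any seasonal change. The actual size of any bias cannot be derived from the documents, because they give neither rates by acuity nor an expected effect. If the true reduction is large, the conclusion would survive without adjustment.

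**What to change.** Keep the crude month 6 versus month 3 reduction and add the following to Table 4 for both spot-check endpoints.

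- **Model.** A patient-level rate model (negative binomial or quasi-Poisson) with log patient-days as offset. Include period, factors fixed at admission (age, sex, BMI, Charlson index, elective or emergency, grouped surgery type) and period-by-acuity terms. Leave out complications and length of stay, which arise after admission and may be affected by monitoring.
- **Standardisation and reporting.** Standardise both periods to one common case mix. Report crude and standardised rate ratios with 95% confidence intervals, and tabulate case mix by period.
- **Decision rule.** Claim the 20% reduction as a Healthdot effect only if the standardised result agrees with the crude one.
- **Data.** Code elective/emergency and surgery type as option lists; both are now open fields. Count spot checks and patient-days by calendar period from the electronic record. The eCRF holds one total per admission, from which stays crossing the switch cannot be split.
- **Definitions.** State whether all checks or only additional ones count.

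The cost is a little more analysis and coding work, since the covariates are already planned. Two limits remain: covariates exist only for consenting patients, and unmeasured differences between the periods cannot be removed.

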4. PROJECT POPULATION

a. Population (base)

Around 10 nurses and 5 physicians, working at the designated surgical ward, will sign informed consent and participate as the primary research population in the core group for in depth analysis regarding the implementation evaluation.

Adults, male or female above 18 years old, admitted to one surgical ward at the Catharina hospital will be included in this prospective cohort study. Admission will mainly concern postoperative patients, but readmissions, clinical observation, treatment of complications or transfers from other departments or the intensive care unit are also reasons for admission. Most of the patients that will be treated at this department receive care of oncological surgical nature, but also general surgical patients, urological and gynaecological patients can be admitted to this department.

This ward has an average annual turnover of approximately 900-1000 patients each year based on the previous three years. A study period of 6 months is proposed to obtain a total of 500 patients in total, 250 patients during each study phase.

b. Inclusion criteria

Nurses and physicians are the primary research population for answering the research objectives.

Nurses and physicians, participating in het focus group will sign informed consent. Nurses working at the surgical ward who will fill in the IWS questionnaire at multiple occasions will sign for informed consent on this questionnaire form (attachment 3) for use of the anonymized data.

Patients won't be included for participation since the Healthdot will be the new standard of care regarding monitoring. Patients will however sign informed consent at admission for use of anonymized data.

Core/focus group

Nurses

- Registered in the national register of medical professions (Big register)
- Appointed as a nurse at the Catharina hospital and working in the surgical department during the study period.
- Willingness to participate in the core group for evaluation of the implementation

Physicians

- Registered in the national register of medical professions (Big register)
- Appointed at the Catharina hospital as a physician or resident.
- Willingness to participate in the core group for evaluation of the implementation

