Nursing team working at this surgical ward will fill in the IWS on a weekly base. Every nurse will consent to the voluntary participation for this one question inquiry and consent to use of the anonymous data. No additional informed consent will be asked to this group.

c. Exclusion criteria

Core/focus group

Nurses & Physicians

- Termination of employment within the study period
- Not willingness to participate in the core group

d. Sample size calculation

Sample size calculation is not applicable for implementation projects. Nevertheless, we expect to obtain data from at least 500 patients, 250 patients during each phase, based on the average annual turnover of approximately 900-1000 patients each year over the previous three years at this ward. Our core group contains out of 10 nurses and 5 physicians.

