- Additional spot check monitoring for blood pressure, oxygen saturation and temperature may be requested by any member of the treatment team

Premature termination of the study

• In the event that the International Workload Scale (IWS) (13) is in the highest category at moment 4-5 for more than 50% of the staff.

d. Withdrawal of individual subjects

Subjects of the core group can leave the study at any time for any reason if they wish to do so without any consequences.

i. Replacement of individual subjects after withdrawal

Participants who withdraw their participation from the core group won't be replaced.

e. Follow-up of subjects withdrawn from treatment

N/A

f. Premature termination of the study

In case the International Workload Scale (IWS) will be in the highest category of this scale for more than 50% of the staff at month 4-5 during phase two of this project.

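### Repeated measures ANOVA for EBPAS discards staff with a missed moment in a small, unreplaced group; a mixed model is a cheap improvement, chiefly against bias

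*Combined protocol and SAP*

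**What the plan says.** - **Test.** The EBPAS row of Table 4 (section 8) treats the scale as continuous and names "Repeated measures ANOVA". The same section sets the software ("All analysis are performed using IBM SPSS Statistics 26.0 for Windows") and the level ("with 95% confidence interval and p < .05 as statistically significant").
- **Moments.** The measurement timetable in section 3 places EBPAS at months 0, 3 and 6. The month 3 entry is marked as items 9-15 only.
- **Group.** Section 4.d: "Our core group contains out of 10 nurses and 5 physicians". Section 4.a says these staff "participate as the primary research population in the core group for in depth analysis regarding the implementation evaluation". No section says outright who completes EBPAS.
- **Leaving.** Section 7.d: "Subjects of the core group can leave the study at any time for any reason". Section 7.d.i: "Participants who withdraw their participation from the core group won't be replaced". Section 4.c also lists as an exclusion "Termination of employment within the study period", without saying what happens to answers already given.
- **Missing forms.** Neither a handling rule nor an expected rate is given.

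**The concern.** The plan allows attrition, does not refill the group, and names a test that in its classical form needs an answer at every moment. A person who misses one form loses their other valid answers too. Those who remain are the people who stayed and always answered. EBPAS is the only adoption instrument, and section 2 expects attitudes to become more positive during implementation. Selective loss therefore bears on the quantity being measured, and a group of this size has few answers to spare.

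**Working it through.** The plan gives no sample size, power or error rate for EBPAS, so there is no figure of its own to reproduce.

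**From the documents:** group 10 + 5 = 15; moments 0, 3 and 6, with month 3 limited to items 9-15; level 0.05.

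**Assumed:** the group of 15 answers EBPAS; a share q of forms is missed independently at each moment (10% and 20% shown); within-person correlation 0.6; true change from month 0 to month 6 of 0.6 SD; two-sided test.

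**Step 1. What deletion leaves.** Items 9-15 at three moments: complete cases 15(1−q)³, answers collected 45(1−q), answers used 45(1−q)³. Full score at two moments: complete pairs 15(1−q)².

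| q | Complete cases, items 9-15 | Answers used / collected | Complete pairs, full score |
|---|---|---|---|
| 5% | 12.9 | 38.6 / 42.8 | 13.5 |
| 10% | 10.9 | 32.8 / 40.5 | 12.2 |
| 20% | 7.7 | 23.0 / 36.0 | 9.6 |
| 30% | 5.1 | 15.4 / 31.5 | 7.3 |

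Even at 5%, the chance that at least one of the 15 is dropped from the three-moment analysis is 1 − 0.95⁴⁵ = 90%. If people only leave, 3 leavers give 15 − 3 = 12 complete cases and 5 give 10.

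**Step 2. Power, complete cases against a random-intercept REML model on all answers (simulated).**

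| Setting | Test | Complete cases | Mixed model |
|---|---|---|---|
| Items 9-15, 10% missed | month 0 to 6 | 50-57% | 64-65% |
| Items 9-15, 20% missed | month 0 to 6 | 36-39% | 54-56% |
| Items 9-15, 10% missed | overall | 43-45% | about 50-52% |
| Items 9-15, 20% missed | overall | 28-31% | 42-46% |
| Leavers only, 20% | month 0 to 6 / overall | 61% / 49% | 64% / 51% |
| Leavers only, one third | month 0 to 6 / overall | 51% / 42% | 56% / 46% |
| Full score, 10% missed | month 0 to 6 | 57% | 58% |
| Full score, 20% missed | month 0 to 6 | 45% | 49% |

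Ranges come from separate simulations. The overall-test values at 46% (mixed model) and 43% (ANOVA) come from the smallest, 400 runs; 42% is the safer mixed-model figure at 20% missed.

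The complete-case contrast can be checked in closed form. The noncentrality is 0.6/√(2(1−0.6)) × √n = 0.671√n, which gives 2.22 for n = 10.9 and 1.86 for n = 7.7. With error pooled over three moments, 2(n−1) degrees of freedom, power is 56% and 41%. With the paired differences alone, n−1 degrees of freedom, it is 52% and 36%. This choice of error term accounts for most of the spread in the complete-case column. For the full score, n = 12.2 and 9.6 give 2.34 and 2.08, and power of about 57% and 45%.

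With no true change and 20% missed, the contrast rejected in 5.3% (complete cases) and 4.8% (mixed model) of 2,000 runs.

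**Step 3. Bias.** Suppose staff with a low month 0 score are more likely to be missing at month 6. For a true change of 0.60 SD, complete cases estimated 0.47 SD in one simulation and 0.51-0.54 in another; the mixed model gave 0.59 and about 0.6. With no true change, complete cases showed −0.11 SD and the mixed model 0.00.

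**The case against.** The other side has a good case on size.

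- **Month 3 is not a full EBPAS.** The three-moment figures hold only for an items 9-15 score. A full score has two moments, where the gain is small. The scored item set must be settled before the choice of model, and a mixed model does not settle it. This stands.
- **The group of 15 is inferred.** Section 7 ties the core group to the thematic analysis, not to EBPAS, and the training text in sections 6 and 7.c speaks of staff more widely. Only the IWS is expressly given to the wider nursing team, so the core group is the natural reading, but it is a reading. A larger group would still lose cases listwise, with less consequence.
- **The withdrawal rule supports only a small gain.** It describes leaving, where the gain is about 2 to 5 points. The larger gains need scattered missed forms, for which the documents give no rate. This stands.
- **The exclusion for ended employment.** Using every answer given sits uneasily with section 4.c and needs reconciling. This stands.
- **Little depends on the p-value.** EBPAS is secondary, has no success threshold, and section 8 introduces staff-level analysis as descriptive. This limits the grade but does not remove the point, since Table 4 does name a test.

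**Conclusion.** The point holds as a cheap improvement to a secondary analysis, between optional and recommended. Loss of partial responders follows from the named test; that it deletes listwise, and that SPSS has a mixed-model procedure, is general knowledge of method and software and not stated in the plan. The power gain is about 1 to 5 points for leavers only or for the full score, and roughly 7 to 20 points for scattered misses on the three-moment score, depending on test and missing rate. The stronger reason is bias. The mixed model protects when loss depends on recorded answers, but not when it depends on unrecorded ones. All sizes rest on the assumed missing rates, correlation and effect, and on 15 respondents.

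A reader might infer three stronger claims that the documents do not support:
- That non-replacement by itself costs the adoption test much of its power. The leaver-only results show otherwise.
- That deletion must flatter the device because enthusiasts remain. When low month 0 scorers are lost, the simulated error runs the other way: improvement is understated.
- That the trial's main conclusions are at risk. The primary endpoints are SUS and spot checks, which this test does not touch.

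**What to change.** In the EBPAS row of Table 4, replace the entry by a linear mixed model (SPSS MIXED, REML; moment fixed, person random; Satterthwaite degrees of freedom) using every answer given. Specify:

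1. The full 15-item score at months 0 and 6, contrast 0 to 6.
2. The items 9-15 score at months 0, 3 and 6, contrasts 0 to 3 and 3 to 6.
3. 95% confidence intervals for each contrast. A 7-item score is never compared with a 15-item score.
4. Who completes EBPAS, with a person code linking the forms (repeated measures ANOVA needs this too).
5. That answers given before withdrawal or end of employment are kept, with section 4.c reworded to agree.

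The cost is an edit to Table 4 and a few sentences in sections 4 and 8, with the same software and no new data. The downside is an assumed covariance structure and approximate degrees of freedom in a small group. Making the change before the answers are analysed avoids a data-driven choice later.
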